**COMPARISON OF THE VALIDITY AND RELIABILITY OF THREE
DIFFERENT METHODS USED FOR WRIST PROPRIOCEPTION
MEASUREMENT**

The most recently revised date: 06.25.2018

**The Human Subjects Protection Review Board
approbation date: 06.25.2018**

STUDY PROTOCOL

Participants

The prior sample size calculation section of G*Power 3.1.9.2 software revealed that the inclusion of 32 healthy participants (64 wrists) was necessary for achieving 95% power. Individuals who suffered an injury or underwent a surgical procedure in the last six months that could affect hand functions or senses were excluded from the study. Additionally, individuals with a history of neuromuscular disease, traumatic nerve injury, congenital anomalies, or skin infections were excluded. An informed consent form was obtained from all participants. An independent ethics committee approved the study (approval number:24074710--028).

Instrumentation

The Cybex isokinetic dynamometer [Cybex NORM®, Humac, CA, USA] was used as a reference standard to test the validity of the universal goniometer, inclinometer [Acumar, Lafayette Instrument Co., Lafayette, USA], and JPSG. The isokinetic dynamometer is a well-known instrument for measuring passive and active joint position sense (AJPS) and provides a target angle result without rater bias (Relph & Herrington, 2015). The Cybex isokinetic dynamometer has a good reliability in evaluating wrist AJPS (Seven et al., 2019).

Procedures

The evaluation of proprioception using the isokinetic dynamometer was performed with the participants in sitting. The shoulder was positioned in the midline, the elbow was flexed about 90°, and the wrist was positioned in supination (Brown, 2000). During the evaluation, the forearm was fixed with a strap to prevent the forearm from moving and changing the angle of the wrist. The rotation axis of the dynamometer was aligned with the diagonal axis of the distal tubercle of radius and the head of ulna (Figure 1). The

wrist was placed in a 0° position. In this starting position, the range of motion was set as 40° flexion and 40° extension (Ellenbecker et al., 2006). The device was calibrated before the evaluation of each participant.

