30° extension, which is the functional position of the wrist, was selected as the target angle for AJPS assessment (Neumann, 2002; Seven et al., 2019). After the test was explained to the participants, they were asked to actively bring the wrist from the neutral (0° flexion/extension) to 30° extension (a barrier was placed at 30° line) and wait for 5 seconds at this position. The participants were then asked to return to the starting position (a block was also placed at 0°). The participants were then asked to find the target angle. This trial was repeated three times. The amount of error between the target and achieved angles were recorded as the absolute angular error. The relative error amount was calculated using the arithmetic mean of these three absolute angular errors (Suner-Keklik et al., 2017). The same measurements were repeated for the other limb. The same rater performed all measurements.

All evaluations were repeated at the same hour of the day, seven days after the first measurement by the same rater to examine the test-retest reliability of the methods (Holmbäck et al., 1999). To avoid the learning effect (Feiring et al., 1990), the order which extremities were assessed (right/left) was determined using a web-based “Random Sequence Generator Application” (<https://www.random.org/sequences/>). The same randomization method was used to determine the order of the evaluation methods. The sequence used for each participant on the first evaluation was repeated on the second evaluation. A five-minute rest period was given between each measurement to eliminate the effect of muscle fatigue. As AJPS was demonstrated to significantly reduce during the menstruation period, the evaluation days of the female participants were arranged not to coincide with the week of menstruation (Aydoğ et al., 2005).

REFERENCES

- Brown LE 2000 Isokinetics in human performance. *Human Kinetics*.

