**COMPARISON OF THE VALIDITY AND RELIABILITY OF THREE
DIFFERENT METHODS USED FOR WRIST PROPRIOCEPTION
MEASUREMENT**

The most recently revised date: 06.25.2018

**The Human Subjects Protection Review Board
approbation date: 06.25.2018**

Statistical Analysis

Statistical analysis was performed using the SPSS version 28 (IBM, Armonk, NY) computer software system. The Normality of the variables was tested using the Shapiro-Wilk test. Since the data were non-parametric, the validity analysis was performed using Spearman's correlation test. The validity of these three methods was calculated according to their correlation with the isokinetic dynamometer data. Correlation coefficients was used to interpret the results. The correlation coefficient was defined as follows: between 0.90-1.00 was very high, between 0.70-0.90 was high, between 0.50-0.70 was medium, between 0.30-0.50 was weak, and less than 0.30 was negligible (Mukaka, 2012). The statistical significance level was determined as $p < 0.05$ for all analyses.

The Intraclass Correlation Coefficients $ICC_{3,1}$ (two-way mixed, absolute agreement) were calculated for test-retest reliability analysis. The $ICC_{2,1}$ value that was greater than 0.90 was defined as an excellent correlation, a good correlation between 0.75 and 0.90, a moderate correlation between 0.50-0.75 and a poor correlation if less than 0.50 (Koo & Li, 2016). Measurement errors of the three methods were used to calculate standard error of measurement (SEM) and Minimal Detectable Change (MDC) in a 95% confidence interval (Haley & Fragala-Pinkham, 2006; Suner-Keklik et al., 2017).

RESULTS

A total of 32 participants (64 wrists) were evaluated in the study (Figure 5). Demographic characteristics are presented in Table 1.

[figure not shown]

Table 1. Demographic features

	Minimum	Maximum	Mean ± S.D.
Age	19.00	31.00	23.34 ± 3.84
Height	160.00	193.00	173.66 ± 8.87
Weight	48.00	115.00	68.31 ± 13.75
BMI	17.56	33.97	22.52 ± 3.29

BMI: Body Mass Index

The results of the validity analysis of the methods are displayed in Table 2. The validity of these methods was found to be weak for the inclinometer and JPSG and moderately for the goniometer (Mukaka, 2012) (Table 2).

Table 2. The results of validity analysis and descriptive statistics of the methods

Methods	Median (25th per – 75th per)	r	P
Isokinetic dynamometer	3.17° (2.33° – 4.83°)	-	-
Inclinometer	3.66° (2.66° – 5.83°)	0.350	0.005*
Goniometer	3.50° (2.33° – 4.66°)	0.529	<0.001*

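### The SAP does not say which session feeds the validity correlations; the printed P values treat 64 wrists from 32 people as independent, and day-7 pairs, if they exist, appear unused

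*SAP*

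**What the plan says.** In the SAP, Statistical Analysis, "the validity analysis was performed using Spearman's correlation test", and "The validity of these three methods was calculated according to their correlation with the isokinetic dynamometer data". No session, and no combination of sessions, is named. Table 2 reports a single r and P per method: inclinometer 0.350 (P 0.005), goniometer 0.529 (P <0.001), JPSG 0.432 (P <0.001). No confidence interval is given for r.

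The Results section states that "A total of 32 participants (64 wrists) were evaluated in the study".

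The Protocol, Procedures, defines the score per limb: "The relative error amount was calculated using the arithmetic mean of these three absolute angular errors". On the retest it says: "All evaluations were repeated at the same hour of the day, seven days after the first measurement by the same rater". The same sentence gives test-retest reliability of the methods as the purpose. SAP Table 3 then shows two-session medians and ICCs for the inclinometer, goniometer and JPSG, and nothing for the dynamometer.

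**The concern.** Validity is one of the two questions in the study title, and the SAP reads each r against bands with cut-points at 0.30, 0.50, 0.70 and 0.90. With 64 pairs each r is imprecise, and with two wrists per person it may be less precise than the printed P implies. If a second set of method-dynamometer pairs exists, it could narrow the intervals and show whether a validity coefficient repeats a week later. The second matter is a live one, because the test-retest ICCs in Table 3 are only 0.114 to 0.422. A reader also cannot tell which scores Table 2 rests on.

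**Working it through.** **Inputs.** r, P, medians and quartiles from SAP Table 2; session medians, quartiles and ICCs from SAP Table 3; 32 participants and 64 wrists from both documents. The dynamometer's ICC, the cross-session correlation and the between-wrist correlation are not given and are assumed below.

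**1. Reproduce the printed P.** Use t = r·√[(n−2)/(1−r²)], two-sided, with r = 0.350 and 1−r² = 0.8775.

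- n = 32: t = 0.350·√(30/0.8775) = 2.05, P = 0.0496
- n = 64: t = 0.350·√(62/0.8775) = 2.94, P = 0.0046, which prints as 0.005
- n = 128: t = 0.350·√(126/0.8775) = 4.19, P = 0.00005

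Only n = 62 to 64 rounds to 0.005. At n = 64 the other two r values give P = 0.000007 and 0.0004, consistent with the printed <0.001. The ICC P values also fit 64 independent wrists: for the inclinometer F = (1+0.114)/(1−0.114) = 1.26 on 63 and 63 degrees of freedom gives P = 0.183, as printed; with 32 units it would be 0.264.

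**2. Try to identify the session.** Median (quartiles), in degrees:

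| Method | Table 2 | Table 3, 1st | Table 3, 2nd |
|---|---|---|---|
| Inclinometer | 3.66 (2.66, 5.83) | 5.33 (3.33, 8.17) | 4.50 (2.83, 6.33) |
| Goniometer | 3.50 (2.33, 4.66) | 3.50 (2.33, 5.66) | 3.66 (2.33, 4.83) |
| JPSG | 2.50 (1.66, 3.33) | 2.33 (1.33, 3.33) | 2.00 (1.33, 3.33) |

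No row of Table 2 equals either session. A pool of both sessions is excluded for the inclinometer and JPSG, because a pooled median must lie between the two session medians. A two-session mean per wrist is implausible for the inclinometer, whose median and both quartiles lie below those of both sessions.

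**3. Precision of the printed r.** On the Fisher z scale, take the Spearman SE = √[(1+r²/2)/(n−3)] and the 95% interval tanh(atanh r ± 1.96·SE). The n = 32 column is the limiting case in which a person's second wrist adds nothing.

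| Method | SE, n = 64 | Interval, n = 64 | Interval, n = 32 |
|---|---|---|---|
| Inclinometer | 0.132 | 0.11 to 0.55 | −0.01 to 0.63 |
| Goniometer | 0.137 | 0.31 to 0.70 | 0.20 to 0.75 |
| JPSG | 0.134 | 0.20 to 0.62 | 0.08 to 0.69 |

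The between-wrist correlation is not reported, so the truth lies somewhere between these columns.

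**4. Gain from a second session, if there is one.** Simulate multivariate normal scores for 64 wrists in two sessions, with the printed r and ICC of each method, a dynamometer ICC of 0.3 to 0.9, and a cross-session method-dynamometer correlation of 0 to 90% of its ceiling, min(r, √(ICC of method × ICC of dynamometer)). The SE of the mean of the two Fisher z values, divided by the SE of one, is:

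| Method | Wrists independent | Wrists strongly correlated (0.9 of the stable component) |
|---|---|---|
| Inclinometer | 0.71 to 0.75 | 0.71 to 0.79 |
| Goniometer | 0.73 to 0.86 | 0.76 to 0.89 |
| JPSG | 0.73 to 0.85 | 0.75 to 0.89 |

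Allowing for simulation error, the ratio runs from about 0.71 to 0.90, so intervals would be 10% to 29% narrower. In equivalent wrists that is 64/0.90² = 79 to 64/0.71² = 127. Correlating two-session mean scores instead gains almost nothing (SE ratio about 0.93 to 1.16) and estimates a different quantity.

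**5. Effect on the labels.** Apply mid-range ratios of 0.725, 0.78 and 0.77 to the n = 64 SEs in step 3, and suppose that the pooled r equals the printed one:

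- Inclinometer: 0.18 to 0.50, still negligible to weak
- Goniometer: 0.36 to 0.66, still weak to medium
- JPSG: 0.25 to 0.58, still negligible to medium

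These intervals treat wrists as independent and are therefore on the optimistic side.

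**The case against.** The strongest objection is that the second dynamometer session may not exist. Its only support is the Protocol's statement that all evaluations were repeated, and that sentence ties the repeat to the reliability of the methods. The title counts three methods, and the dynamometer is the reference standard, with its reliability taken from a citation. Tables 3 and 4 omit it, and SEM and MDC are for the three methods only. This stands, and it makes the pooling conditional. Against it, the Protocol calls the dynamometer procedure an evaluation and exempts nothing from the repeat.

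A reader might infer that half of the paired validity data was discarded. The documents do not support that as a fact. The same mismatch that makes a two-session mean implausible also means that Table 2 is neither session as printed in Table 3, so what was left out cannot be stated. Nor would a second session double the information: sessions are nested in wrists and wrists in 32 people, and 128 pairs treated as independent would overstate precision further.

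Estimating concurrent validity in one session and using the repeat for reliability is a legitimate design. The size of the gain also rests on quantities that are not printed, on normal scores although the SAP calls the data non-parametric, and on combining r from Table 2 with ICCs from Table 3, which do not describe the same scores. All of this stands and limits the point to one of precision. None of it answers the unnamed session, the unreconciled tables or the missing participant-level interval.

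**Conclusion.** The point holds as a conditional improvement. Three parts are firm: the SAP names no session for the validity scores, Table 2 does not agree with either session in Table 3, and the printed P values fit 64 wrists treated as independent. That the day-7 pairs exist and went unused is the natural reading of the Protocol, but it remains an inference.

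If they exist, pooling the session-specific r values should narrow the intervals by roughly 10-29%, given the assumed dynamometer ICC and the assumed cross-session and between-wrist correlations. A reader might expect this to settle how valid each method is. On the figures above it probably would not: each interval would still cross at least one cut-point. The need for a participant-level interval does not depend on whether the dynamometer was repeated.

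**What to change.** In the SAP validity paragraph:

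1. State which session's scores feed Table 2, and reconcile its medians and quartiles with Table 3.
2. If the dynamometer was repeated at day 7, report Spearman's r for each session and their pooled value (mean of the two Fisher z values, back-transformed). Correlating within session keeps the target as the validity of a single-session score.
3. In either case, give a 95% confidence interval for each r from a bootstrap that resamples participants, keeping both wrists, and both sessions where used, together.
4. If the dynamometer was not repeated, say so in the Protocol's Procedures section; step 2 then falls away.

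The cost is a modest reanalysis and a few extra columns in Table 2, with no new participants. The downside is that a pooled r averages over any practice effect between sessions; the two session values printed beside it would show this. Participant-level intervals may also be wider than the present P values suggest.

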JPSG	2.50° (1.66° – 3.33°)	0.432	<0.001*

per: percentile, r: correlation coefficient, °: degree, *: p<0.05

The results of the test-retest reliability analysis of the methods are displayed in table 3. The inclinometer was not found to be a reliable method for evaluating AJPS while the goniometer and JPSG were detected to have significant test-retest reliability. However, the 95% confidence intervals of the goniometer and JPSG were poor (Koo & Li, 2016) (Table 3).

Table 3. The results of test-retest reliability analysis and descriptive statistics

Methods	1st Measurement	2nd Measurement	ICC_{3,1}	P	SE M	MDC
	Median	Median				
	(25 per – 75 per)	(25 per – 75 per)				
Inclinometer	5.33° (3.33° – 8.17°)	4.50° (2.83° – 6.33°)	0.114	0.183	0.11	0.25
Goniometer	3.50° (2.33° – 5.66°)	3.66° (2.33° – 4.83°)	0.422	<0.001*	0.32	0.75
JPSG	2.33° (1.33° – 3.33°)	2.00° (1.33° – 3.33°)	0.369	0.001*	0.29	0.68

(per: percentile, r: correlation coefficient, °: degree, *: p<0.05)

The order in which each method was evaluated is presented in Table 4.

Table 4. The sequences of methods

Methods	First	Second	Third
Goniometer	23 (% 35.9)	24 (% 37.5)	17 (% 26.6)
Inclinometer	19 (% 29.7)	20 (% 31.2)	25 (% 39.1)
JPSG	22 (% 34.4)	20 (% 31.2)	22 (% 34.4)

REFERENCES

- Haley SM, Fragala-Pinkham MA 2006 Interpreting change scores of tests and measures used in physical therapy. *Physical therapy* 86, 735-743.
- Koo TK, Li MY 2016 A guideline of selecting and reporting intraclass correlation coefficients for reliability research. *Journal of chiropractic medicine* 15, 155-163.
- Mukaka MM 2012 A guide to appropriate use of correlation coefficient in medical research. *Malawi Medical Journal* 24, 69-71.

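### All six SEM and MDC values in SAP Table 3 are wrong: they appear to use the ICC where the SD belongs, and a 90% rather than a 95% multiplier

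*SAP*

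**What the plan says.** The Statistical Analysis section of the SAP promises, for each of the three methods, the "standard error of measurement (SEM) and Minimal Detectable Change (MDC) in a 95% confidence interval". It gives no formula and cites two papers for the approach. The ICC is described as "two-way mixed, absolute agreement) were calculated for test-retest reliability analysis". The same section justifies rank correlation for the validity analysis with "Since the data were non-parametric".

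Table 3 in the SAP Results gives medians and quartiles in degrees for each session, then the ICC, its P value, the SEM and the MDC. The last two carry no unit, and no SD is reported. For the inclinometer, session 1 reads "5.33° (3.33° – 8.17" (degrees) and session 2 reads "4.50° (2.83° – 6.33" (degrees). The text below the validity results says: "The inclinometer was not found to be a reliable method for evaluating AJPS". The analysis set is described as "A total of 32 participants (64 wrists) were evaluated in the study".

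**The concern.** An SEM is a standard deviation of measurement error, in the units of the score, which here are degrees. It is normally SD × √(1 − ICC). With an ICC of 0.114, almost all of the inclinometer's spread is error, so its SEM should be close to its SD. Yet the interquartile ranges are 4.84° and 3.50°, and the printed SEM is 0.11.

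The ordering is also odd. The method with the lowest ICC and the widest quartiles has the smallest SEM and MDC.

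The MDC tells a user how large a change must be before it exceeds measurement error. If it is several times too small, changes well inside the error will be taken as real. For scale, the inclinometer's group median moved from 5.33° to 4.50° between sessions. That is 0.83°, more than three times its printed MDC of 0.25. SEM and MDC are named outputs of this reliability study, so errors in them matter to its users.

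**Working it through.** The order throughout is inclinometer, goniometer, JPSG.

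**Inputs (SAP, Results, Table 3).**

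| | Session 1 quartiles | Session 2 quartiles | ICC | SEM | MDC |
|---|---|---|---|---|---|
| Inclinometer | 3.33–8.17 | 2.83–6.33 | 0.114 | 0.11 | 0.25 |
| Goniometer | 2.33–5.66 | 2.33–4.83 | 0.422 | 0.32 | 0.75 |
| JPSG | 1.33–3.33 | 1.33–3.33 | 0.369 | 0.29 | 0.68 |

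**Step 1: reproduce the printed figures.**

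- ICC × √(1 − ICC) = 0.114 × 0.941, 0.422 × 0.760, 0.369 × 0.794 = 0.107, 0.321, 0.293. These round to the printed SEMs.
- Multiplying by 1.645 × √2 = 2.326 gives 0.250, 0.746, 0.682. These round to the printed MDCs.
- Multiplying by 1.96 × √2 = 2.772 gives 0.30, 0.89, 0.81. None match.

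**Step 2: the stated 95% level.** A two-sided 95% MDC requires MDC/SEM = 2.77. Allowing for rounding of both columns, the printed ratios can only lie in these ranges:

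- Inclinometer: 0.245/0.115 to 0.255/0.105 = 2.13–2.43
- Goniometer: 0.745/0.325 to 0.755/0.315 = 2.29–2.40
- JPSG: 0.675/0.295 to 0.685/0.285 = 2.29–2.40

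All three exclude 2.77 and include 2.33. This conflict needs no assumption about how the SEM was obtained.

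**Step 3: the smallest SD the quartiles allow.** At least 25% of values lie at or below Q1 and at least 25% at or above Q3. The variance is therefore at least 0.5 × (IQR/2)², so SD ≥ IQR/2.83 for any distribution. Pool the two sessions by root mean square:

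| | IQRs | Pooled IQR | SD ≥ | SEM ≥ | MDC95 ≥ | MDC95 floor / printed MDC |
|---|---|---|---|---|---|---|
| Inclinometer | 4.84, 3.50 | 4.22 | 1.493° | 1.41° | 3.90° | 15.6 |
| Goniometer | 3.33, 2.50 | 2.94 | 1.041° | 0.79° | 2.19° | 2.9 |
| JPSG | 2.00, 2.00 | 2.00 | 0.707° | 0.56° | 1.56° | 2.3 |

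Here SEM = SD × √(1 − ICC) and MDC95 = 2.772 × SEM. The SEM floors are 12.8, 2.5 and 1.9 times the printed SEMs.

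**Step 4: the same conflict read backwards.** The printed SEMs would need SDs of 0.12°, 0.42° and 0.37° (SEM/√(1 − ICC)). The floors for the narrower session alone are 1.24°, 0.88° and 0.71°. At the pooled SD floors, the printed SEMs would instead require ICCs of 1 − (SEM/SD)² = 0.995, 0.906 and 0.832, or 0.994, 0.903 and 0.826 with each SEM at its upper rounding limit. The table prints 0.114, 0.422 and 0.369.

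**Step 5: other choices of SD.**

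| SD taken from | MDC95 floor / printed MDC |
|---|---|
| Session 1 only | 17.9, 3.3, 2.3 |
| Session 2 only | 12.9, 2.5, 2.3 |
| Table 2 quartiles (IQRs 3.17, 2.33, 1.67) | 11.7, 2.3, 1.9 |

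**Step 6: a rough central estimate.** If SD = IQR/1.349, which is exact only for normal data, the pooled Table 3 figures give SEM of about 2.9°, 1.7° and 1.2°, and MDC95 of about 8.2°, 4.6° and 3.3° (33, 6 and 5 times the printed MDCs). Either session alone gives MDC95 of 6.8–9.4°, 3.9–5.2° and 3.3°. Table 2 gives 6.1°, 3.6° and 2.7°. The SAP itself treats the data as non-normal, so these are only indications.

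**The case against.** The strongest reply is that the SAP prints no formula, so the factors 15.6, 2.9 and 2.3 depend on a convention it never adopts: SEM = SD × √(1 − ICC) with the session SDs pooled. That is correct, and the factors should be read with that condition. But no reasonable alternative rescues the table.

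- **Another session or table.** The floors in Step 5 still leave every printed MDC too small. Table 2 is a weak check in any case: its inclinometer row, "3.66° (2.66° – 5.83" (degrees), matches neither session in Table 3, and the SAP does not say why.
- **A consistency-type SEM** (square root of the error mean square), which leaves out a shift between sessions. With an assumed shift of 0.5° in the means, the floors are still 15.7, 2.8 and 2.1 times the printed MDCs.
- **SEM meaning standard error of the mean.** With 64 wrists, the inclinometer SD would be 0.11 × 8 = 0.88°, below its floor of 1.24°.
- **The multiplier.** 1.645 is also the one-sided 95% value. A confidence interval is naturally read as two-sided, and the choice accounts for only 1.96/1.645 = 1.19. Even at the 90% level, the pooled floors are 13.1, 2.5 and 1.9 times the printed MDCs.

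Two limits stand. The substitution of the ICC for the SD is inferred from the arithmetic, and the six matches are not independent, because the MDCs are a constant times the SEMs. Also, the Results text rests its conclusions on the ICCs and never interprets the SEM or MDC, which bounds the damage within the document itself.

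**Conclusion.** The concern holds. All six SEM and MDC values in Table 3 are wrong as printed. The MDC/SEM ratios contradict the stated 95% level on any reading of an interval. Under SEM = SD × √(1 − ICC) with sessions pooled, the table's own quartiles put MDC95 at no less than 3.9°, 2.2° and 1.6°. This floor requires no distributional assumption. It also remains a valid floor if the SD is defined to include the shift between sessions, because that can only enlarge the SD.

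The true values are probably larger still, with JPSG likely smallest and the inclinometer largest. That would remove the inclinometer's apparent advantage. The quartiles give only lower bounds, so the raw data are needed for the actual figures and to confirm the order.

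This error does not by itself alter the ICCs, their P values or the reliability conclusions in the text.

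**What to change.** In the SAP's Statistical Analysis section, state one definition that fits the absolute-agreement ICC: SEM = SD × √(1 − ICC), in degrees, with the SD taken over the scores of both sessions together so that a shift between sessions counts as error, and MDC95 = 1.96 × √2 × SEM. An SEM computed directly from the ICC model's variance components would also serve, provided the SAP says so and says whether the session shift is included.

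Report the SDs. Recompute both columns of Table 3 from the raw data, print the unit and the confidence level, and withdraw the current values.

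The cost is a sentence or two of wording and a short re-analysis of data already collected. The reported measurement errors will be larger and less favourable to all three methods.

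### Validity grades rest on the point estimate of Spearman r alone; the 95% intervals cross two or three of the SAP's bands, so neither a grade nor a difference in grade is established

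*SAP*

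**What the plan says.** SAP, Statistical Analysis: "the validity analysis was performed using Spearman's correlation test", each method being correlated with the isokinetic dynamometer. The section then states "Correlation coefficients was used to interpret the results" and lists the bands: below 0.30 negligible, 0.30 to 0.50 weak, 0.50 to 0.70 medium, 0.70 to 0.90 high, 0.90 to 1.00 very high. The inferential rule is "The statistical significance level was determined as $p < 0.05$ for all analyses". No interval for r is planned.

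SAP, Results, Table 2 gives r and P only: inclinometer 0.350 (P 0.005), goniometer 0.529 (P < 0.001), JPSG 0.432 (P < 0.001), each with an asterisk for significance. The validity conclusion is the band label: "The validity of these methods was found to be weak for the inclinometer and JPSG and moderately for the goniometer". *Moderately* is not a band name in the SAP; it is read here as *medium*.

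On sample size, the Protocol (Participants) says that "the inclusion of 32 healthy participants (64 wrists) was necessary for achieving 95% power". It gives no test, effect size, null value, sidedness or unit of analysis. The SAP confirms the number: "A total of 32 participants (64 wrists) were evaluated in the study".

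**The concern.** The label is the study's validity conclusion, and it is what a reader choosing a tool will take away: one method one grade above the other two. The bands at issue are 0.20 wide. If the sampling error of r is of the same order or larger, the label reports where the estimate happened to fall, not what the data show about the method.

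The P column does not fill that gap. It answers whether r differs from zero, and an asterisk is compatible with a correlation in the SAP's lowest band. Nothing else in Table 2 tells the reader how firmly a grade is supported, or whether the step from *weak* to *moderately* is more than noise.

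**Working it through.** **Inputs.** r and P from SAP Table 2; bands from SAP Statistical Analysis; n = 64 wrists from 32 participants (Protocol, Participants; SAP, Results).

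**1. Reproduce the P values.** t = r·√((n − 2)/(1 − r²)), two-sided, n − 2 degrees of freedom.

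| Method | r | t, n = 64 | P, n = 64 | P, n = 32 | Table 2 |
|---|---|---|---|---|---|
| Inclinometer | 0.350 | 2.94 | 0.0046 | 0.050 | 0.005 |
| JPSG | 0.432 | 3.77 | 0.0004 | 0.014 | <0.001 |
| Goniometer | 0.529 | 4.91 | <0.0001 | 0.002 | <0.001 |

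Only n = 64 matches, so the wrists were analysed as independent.

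**2. What P < 0.05 requires.** The critical t on 62 degrees of freedom is 1.999, so the critical r is 1.999/√(62 + 1.999²) = 0.246. This lies in the *negligible* band.

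**3. Intervals at n = 64.** Fisher z with the Bonett-Wright variance for Spearman's r: SE = √((1 + r²/2)/(n − 3)); limits tanh(atanh r ± 1.96·SE).

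| Method | atanh r | SE | 95% CI | Width | Bands covered |
|---|---|---|---|---|---|
| Inclinometer | 0.365 | 0.132 | 0.11 to 0.55 | 0.45 | negligible, weak, medium |
| JPSG | 0.462 | 0.134 | 0.20 to 0.62 | 0.42 | negligible, weak, medium |
| Goniometer | 0.589 | 0.137 | 0.31 to 0.69 | 0.38 | weak, medium |

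Each interval is about twice the width of a band. Plain Fisher z (SE = 1/√(n − 3)) gives 0.11 to 0.55, 0.21 to 0.61 and 0.33 to 0.69, with the same bands covered.

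**4. Two wrists per person.** The documents do not give the within-person correlation ρ. As a rough illustration, take an effective n of 64/(1 + ρ) in the same formula.

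| Assumed ρ | Effective n | Inclinometer | JPSG | Goniometer |
|---|---|---|---|---|
| 0 | 64 | 0.11 to 0.55 | 0.20 to 0.62 | 0.31 to 0.69 |
| 0.5 | 42.7 | 0.04 to 0.60 | 0.14 to 0.66 | 0.25 to 0.73 |
| 1 | 32 | −0.01 to 0.63 | 0.08 to 0.69 | 0.20 to 0.75 |

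In the last two rows the goniometer interval runs from *negligible* to *high*.

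**5. Difference between methods.** Overlapping intervals are not a test, and the three correlations share the dynamometer readings. The Meng test for dependent correlations needs the correlation rₓ between the two methods, which is not reported, so a range of 0 to 0.8 is assumed (n = 64, independent wrists):

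z = (atanh r₁ − atanh r₂)·√((n − 3)/(2(1 − rₓ)h)), where h = (1 − f·m)/(1 − m), f = (1 − rₓ)/(2(1 − m)) and m = (r₁² + r₂²)/2.

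- Goniometer v JPSG: difference in z 0.126, m = 0.233. With rₓ = 0, h = 1.106, z = 0.66, P = 0.51. With rₓ = 0.8, h = 1.264, z = 1.39, P = 0.17.
- Goniometer v inclinometer: difference in z 0.223, m = 0.201. With rₓ = 0, h = 1.094, z = 1.18, P = 0.24. With rₓ = 0.8, h = 1.220, z = 2.50, P = 0.01.

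The goniometer and JPSG are not separated anywhere in this range. For the inclinometer the answer depends on the unreported rₓ.

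**The case against.** The bands are set out in the SAP, the three labels match the three estimates, and classifying an estimate descriptively is not an inferential claim. The verdicts are modest: no method is called highly valid, and with independent wrists all three upper limits stay below 0.70, so the intervals do not overturn that reading. All of this stands. The labels are not wrong. What does not follow is that a description of the estimate can serve, unqualified, as the conclusion about the method, or that a one-band step separates methods.

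It may also be said that if a grade could be stated only when the interval lies inside one band, *weak* and *medium* could never be awarded at n = 64. That is true, and no such rule is proposed. Nor do the documents supply a minimum correlation for calling a method valid, so none is proposed either.

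A reader might infer that the 95% power can refer only to rejecting r = 0 at a weak correlation, and so that the study was sized merely to detect weak validity. The documents do not support this. The Protocol names the software ("The prior sample size calculation section of G*Power 3.1.9.2 software") but not the test, effect size, null value, sidedness or unit, and does not tie the figure to validity rather than reliability. At two-sided 5%, 95% power against zero corresponds to r of about 0.43 with 64 independent pairs but about 0.58, a *medium* value, with 32. With 64 pairs it also fits r of 0.65 against a null of 0.3, or a paired t-test with a standardised difference of 0.46. The calculation cannot be identified.

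**Conclusion.** The point holds as one of missing precision, not of wrong labels. With independent wrists, the assumption most favourable to the plan, the intervals cover three bands for the inclinometer and JPSG and two for the goniometer. No grade is established for any method. The data do not separate the goniometer from the JPSG at any assumed inter-method correlation from 0 to 0.8, and the reported figures cannot show whether they separate it from the inclinometer.

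The intervals rest on a large-sample approximation for Spearman's r. Positive dependence between a person's wrists would widen them; by how much is an assumption here (for the goniometer, about 0.25 to 0.73 if the effective n is about 43).

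The statement that the sample "was necessary for achieving 95% power" cannot be cited as support for the grading, because its inputs are not given. Nothing stronger can be said about what it was meant to show.

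**What to change.** In SAP Statistical Analysis, plan a 95% confidence interval for each Spearman r from a bootstrap that resamples the 32 participants, keeping both wrists of a person together, and add it as a column in Table 2.

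In Results, keep the band as a description of the estimate and state in the conclusion the range of bands that the interval covers. On the approximate intervals above, the JPSG would read: r = 0.432, weak by the estimate, interval compatible with negligible to medium. Do not rank the goniometer above the JPSG or inclinometer on the label alone. If a ranking is wanted, the same bootstrap samples give an interval for each difference in r.

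Do not cite the 95% power in support of the grades. If the sentence stays in Participants, give the inputs actually used (test, effect size, null value, sidedness and unit) and do not back-calculate them.

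The cost is some SAP wording, one table column and a re-analysis of data already held. The downside is that the validity verdicts become less definite.
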